1.1 Primary Objective

To assess the feasibility of a novel, weekly supervised virtual health-assisted physical therapy plus relaxation intervention delivered to older adults with advanced thoracic malignancy (N=20). The overall goal is to be able to pilot this intervention targeting modifiable risk factors for worsening functional status: physical performance and negative mood.

1.2 Hypothesis

We hypothesize that we will be able to accrue 20 older adults (≥ 60 years) with a thoracic malignancy and implement a 12-week virtual health-assisted physical activity + relaxation intervention program with biospecimen collection. We hope to achieve 70% adherence to all sessions and a total patient retention rate of 60% at the end of the 12 – week intervention program.

2.0 BACKGROUND AND RATIONALE

2.1 Lung Cancer in Older Adults

Lung cancer is a disease that disproportionately affects older adults as the median age of diagnosis is 70 years.¹ This is important because older adults are the fastest growing demographic in not only the United States but worldwide.² However, this population is significantly under-represented in clinical trials that examine outcomes of new lung cancer drugs.³ This is particularly relevant due to the approval of novel cancer drugs called immune checkpoint inhibitors (Immunotherapy: IO; e.g. pembrolizumab, atezolizumab). The new standard of care for first-line treatment for either advanced non-small cell lung cancer (NSCLC) or small cell lung cancer (SCLC) includes combination of chemotherapy plus IOs,^{4,5} affecting 2/3rds of patients with advanced disease. The effect on older adult's functional status and their ability to complete basic activities of daily living (ADLs) while on these new treatment plans is still widely unknown. This lack of information on how these new treatments may affect older adult's functional status maintains feelings of uncertainty regarding treatment plans.

2.2 Functional Decline + Resiliency

Functional status and resiliency are patient-centered outcomes that should be prioritized in research among older adults with cancer.⁶ Functional status refers to the behaviors needed for an individual to maintain an independent lifestyle. It is defined as an individual's ability to perform basic activities of daily living,⁷ instrumental activities of daily living⁸, and mobility⁹. The majority of older adults with a chronic disease, including cancer, prioritize remaining functionally independent over survival.¹⁰ Even so, functional status is not a primary endpoint in oncology research.¹¹ Resiliency among patients with cancer can be defined as the ability to recover one's functional status after an intervening health care event, e.g. treatment, toxicity, disease progression.¹² Resiliency is important because it demonstrates one's ability to "bounce

“back” from a stressor or intervening event. Resiliency is incompletely understood among patients with lung cancer.

2.3 Targeted Interventions

Poor physical performance and negative mood are two risk factors for a decline in functional status.⁹ Targeted interventions to address these two risk factors with the goal of improving functional status and resiliency are urgently needed. Physical therapy^{13,14} and relaxation interventions¹⁵ (i.e. progressive muscle relaxation) are two such interventions that can improve symptoms and quality of life for patients with cancer.

3.0 METHODS

3.1 Study Overview

This is a prospective, longitudinal study of 20 adults ≥ 60 years of age with advanced thoracic malignancy (NSCLC or SCLC) who plan to receive either immunotherapy and or chemotherapy treatment from the OSUCCC Thoracic Oncology clinic. This cohort is a 12-week pilot intervention consisting of a physical therapy and progressive muscle relaxation program delivered to older adults with advanced lung cancer. Functional trajectories and resiliency will be characterized in this cohort. Enrolled patients will participate in in-person physical therapy and progressive muscle relaxation sessions that are incorporated into routine treatment visits as well as performed via virtual health on the non-treatment weeks. Patients’ functional status will be assessed every 3 weeks and clinical outcomes will be evaluated every 6 weeks. Correlative biomarkers will also be assessed through blood and stool sample collection. Patient follow up will continue through 24 months post enrollment for 1 year and 2 year overall survival.

3.2 Patient Selection

Patients diagnosed with a thoracic malignancy age ≥ 60 will be recruited from the OSUCCC Thoracic Oncology Clinic. Patients who plan to receive either immunotherapy and/or chemotherapy treatment at the James OSUCCC Thoracic Oncology Clinic will receive information regarding the study via physician’s referral. Those individuals agreeing to participate will sign the study consent which includes the HIPAA authorization. Patients who sign the informed consent will be assigned a unique study ID.

Failed screening will be captured as a part of feasibility analysis. Reasons for patient decline will be noted and tracked without the use of patient identifiers.

3.3 Inclusion Criteria

- Age ≥ 60
- Diagnosed with advanced lung cancer: unresectable stage IIIA, IIIB, or stage IV NSCLC or extensive stage SCLC
- Intent to receive treatment from the OSUCCC Thoracic Oncology Clinic
- Patients are eligible at any time point during their treatment here at OSU. Rationale for this timeframe is due to the overwhelming nature of the first few visits and uncertainty

around an eventual treatment plan. Patients at any stage of their treatment can participate and benefit from a physical therapy and psychosocial intervention. Patients will be approached at their initial visit but we can also offer enrollment at any one of the patients regularly scheduled clinic visits. .

- Ability to understand and willingness to sign an informed consent document (or indicate approval or disapproval by another means).

3.4 Patient Exclusion Criteria

- Prisoners are excluded from participation
- There is **NO** exclusion criteria pertaining to ECOG performance status, laboratory values, prior cancer diagnoses, presence of comorbidities or brain metastases.

3.5 Informed Consent

Discussions between the study coordinators and/or treating physician and study participants will occur in the regular Thoracic Oncology Clinic setting. The study coordinators will address all questions regarding the study outline and that participation is voluntary and the participant can withdraw from the study at any time. If eligible patients are interested, study compensation including the virtual health equipment will then be explained to ensure no unethical coercion led to the patient enrollment. If eligible patients decide to participate in the study they will sign the consent form, be assessed for eligibility and, when applicable, register as detailed below.

In the case of natural disasters or pandemic reasons there will be the option for the informed consent to be performed through the telephone. The research coordinators will follow a script [APPENDIX T]. If the patient is interested in the study the ICF will be sent through REDCap to the patients email. REDCap allows for electronic signature. The research coordinator will walk through the consent form with the patient at this time.

3.6 Inclusion of Women and Minorities

Both men and women and members of all races and ethnic groups are eligible for this study.

4.0 STUDY DESIGN

4.1 Overview of Study Design

This is a prospective longitudinal study of 20 adults older than 60 years who have been diagnosed with a thoracic malignancy who intend to receive treatment at the Ohio State University. Eligible participants will undergo the informed consent process. With IRB and participant permission, demographic information will be collected on potential participants who decline enrollment in the study by use of a non-enrollment survey [Appendix A].

[figure not shown]
Participants will undergo treatment prescribed by the treating physician as per standard of care. In addition, patients will undergo an in-person and virtual health physical therapy program. The

in-person program will include a 10-minute cardiovascular warm up on a portable exercise peddler, using either their upper or lower extremities depending on patient abilities. The warm up will be followed by a resistance training module using exercise resistance bands. This is designed to strengthen the core and upper/lower extremities. The workout will end with full body stretches that are held for 30 seconds each. The virtual health visits will include the exact same regimen and equipment as the in-person visits. The portable peddler and resistance bands will be given to the patients either in clinic or mailed to their home based on patient preference.

In addition to the physical therapy program, participants will undergo progressive muscle relaxation (PMR) performed by research graduate students (MA and PhD level) in clinical psychology. The patient is taught to systematically tense and release 16 different muscle groups. Patients will be seen during their regularly scheduled clinic visits and with virtual health “check-ins” in the off-treatment weeks.

Patients enrolled in this study will complete baseline assessments consisting of demographic information, disease assessment, functional status assessments, depression/anxiety screenings, a quality of life measure, toxicity assessment, as well as a physical performance and an endurance test. A study coordinator will assess functional status every 3 weeks either in person, by phone, or virtual health monitoring. Participants’ clinical outcomes will be collected every 6 weeks during their regularly scheduled clinic visits (baseline, 6 weeks, 12 weeks, and 24 week time points). Triggered assessments will be collected on patients with any presence of disease progression, a new toxicity grade, fall, or healthcare utilization such as emergency department visit, inpatient admission, or worsening functional status on either survey. The study intervention will last approximately 12 weeks (3 months). If a patient cancels due to scheduling conflicts or treatment fatigue they will be given the option to reschedule their visit. At the end of the 12 weeks if a patient is still benefiting from PT then those missed visits can be scheduled out. Study assessments will still take place at 12 weeks in an effort to control for time-varying confounders. In the case a patient does make up any visits beyond the study 12 week time period there will be an additional study visit that takes place. This will be an “end of treatment” visit rather than a 12 week visit. The same study assessments performed at baseline will be completed at this time. The patients will be followed until 24 months post-enrollment for 1-year and 2-year overall survival. An additional qualitative assessment will be conducted on those patients that are agreeable and consent to being either video or voice recorded. Patients will participate in a semi-structured interview to assess overall study acceptability. This assessment will help capture the “joy” our novel supportive care intervention brings to the patient, patient’s family, and clinic team.

Figure 1. Study Schema

4.2 Physical Therapy Intervention

The Physical Therapy Intervention will include a total of 12 weeks with one PT visit per week virtually or in-person depending on in-person clinic limitations due to pandemic or natural disasters. Week 1 assessment will be during an in-person visit with physician team within the OSU Brain and Spine Hospital. The other weekly visits will occur through virtual health monitoring at the best availability of the patient and Physical Therapist. There will be a final visit during week 13 where participants undergo the same assessments as the baseline visit as a routine usual care physical therapy discharge visit. The VH visits will be billed as research or as standard-of-care depending on insurance reimbursement changes for VH visits.

The exercise intervention will begin with a 10 minute warm-up using a portable exercise peddlers either using the patient's feet or arms, depending on their mobility and pain status. For example, if the patient is non-ambulatory and does not have the use of their legs, they will be instructed in peddler use with their arms. The Core exercises will include; seated posterior pelvic tilts and seated without back support seated marches. The resistance training exercises will include shoulder press, tricep extension, bicep curls, upper extremity side raises, chest press, calf raises, marches, standing side leg lifts, leg extension in standing, seated knee extension and clamshells. These will be done in 2 sets of 10 reps using resistance bands appropriate for patient's level of fitness. The cool-down portion will include stretches targeting upper extremities (chest, shoulders, and triceps), lower extremities (calves, quadriceps, and hamstrings) and trunk. Each stretch will be held for 30 seconds each. At week 1 visit patient will receive exercise packet including handouts for above therapeutic exercises three resistance bands (yellow, red and green) in order to progress resistance at home based on patient feedback. The physical therapist will educate and demonstrate appropriate use of the equipment during virtual visits or in-clinic visits depending on encounter type. In order to evaluate how hard the participant is working during the virtual health visits; the relative perceived effort (RPE)¹⁶ will

be used with a target goal of 12-14 on the Borg Rating Scale.¹⁷ This indicates a moderate level of intensity.

An exercise log in the patient's electronic medical record will be filled out after each workout to keep track of patient progress. The patient will first be prescribed weekly sessions, then it will increase to twice weekly, then three times weekly based on patient behavior and activity tolerance. One session per week will be supervised virtually or in-person by the physical therapist. Additional sessions will be done by the patient on their own per standard-of care physical therapy practice. During the virtual health sessions, the physical therapist will assess barriers to doing their physical therapy and will problem solve with the patients on how to improve adherence. Please see [Appendix B] for a detailed description of the study exercise log.

Physical Therapy Safety Procedures

Upon the initial in-person visit the physician team or physical therapist will perform a standard-of-care safety screening of pulse oximetry assessment, heart rate and blood pressure monitoring, asking if patient has cardiac or pulmonary history. This screening will take into account if the patient is on oxygen, wears glasses or hearing aids. The in-person visit will also determine the location of the VH physical therapy, their emergency contact, and will verify their home address. It will be recommended that the patient perform their physical therapy in the same location each time. The physical therapist will perform a VH safety checklist at the beginning of each session. This checklist may include but not limited to the following questions:

- Where are you currently located?
- Is anyone else home with you?
- Is your cell phone charged and located near you?
- Have you had any new or different chest pain in the last week?
- Have you had any new or different shortness of breath in the last week?

During the VH visits, similar to an in-person visit, if the patient experiences any sudden chest pain or shortness of breath, they will be instructed to stop the activity, sit-down, and call their emergency contact within the home. If they are unable to call for help or are home alone, the physical therapist will call 911 and will notify the treating physician.

4.3 Progressive Muscle Relaxation

In addition to the exercise intervention, patients will participate in progressive muscle relaxation training at week 1 visit and will undergo “check-ins” each week following either during their regularly scheduled clinic visits (whether in-person or virtually) or through virtual-health study visits. During the training, one of the study psychology graduate students will meet with the patient for approximately 20 minutes. Following the training, the trainer will provide a brief summary of PMR and its efficacy for cancer symptoms. Using the standardized procedures of Bernstein and Borkovec,¹⁸ tension/release procedures for 16 muscle groups are described and demonstrated: right hand and forearm; right bicep; left hand and forearm; left bicep; forehead; upper cheeks and nose; lower cheeks and jaw; neck and throat; chest, shoulders, and upper back; stomach; right thigh; right calf; right foot; left thigh; left calf; and left foot. The trainer will solicit feedback from the patient and all questions will be answered.

ROAR-LCT Study Assessments (Baseline, Weeks 7, 13, and 24)	
Assessment/Test	What it measures
Short Physical Performance Battery (SPPB)	Physical performance
2-6 minute walk test	Endurance
EQ-5D-5L & 16 item Functional activity scale	Functional status surveys
GAD-7	Anxiety Screening
PHQ-9	Depression Screening
PROMIS-10	Quality of Life
Blood & stool sample	Microbiome
Common Toxicity Criteria for Adverse Event (CTCAE v5)	Toxicity
RECIST 1.1 criteria	Disease response
EORTC QLQ C-30 + LC-13	Symptom monitoring
POMS	Symptom monitoring

EQ-5D-5L performed every 3 weeks Not assessed at baseline

PMR is most effective when practiced regularly. To facilitate at-home practice and standardization, patients will also be provided with a PMR CD with standardized shortened versions of PMR and instructions [APPENDIX C] for shortening the 16-muscle-group program to 8 and 4 muscle groups. Additionally, patients will be given a written description of PMR with directions for tensing and releasing each muscle group, following the same sequence of the CD. Individuals are encouraged to practice at home at least 3-5 times per week, and to record the frequency and duration of home practice in a log sheet provided [APPENDIX D].

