4.6 Functional Status Assessments

The Functional Status Assessment survey [APPENDIX G] will be assessed every 3 weeks by the CRC either in person, by phone, by email, or through virtual health monitoring. These surveys will be comprised of 16 activities including seven Activities of Daily Living (ADL) measures⁷, 5 Instrumental Activities of Daily Living (IADL) measures²⁵, and 3 mobility activities.⁹ For each activity, disability is defined as the need for personal assistance or inability to perform the activity. Activities are scored as 0 being no help, 1 being with help, and 2 meaning unable to perform the activity. Higher scores indicate greater disability or a lower functional status. The ADL trajectories will include; eating, grooming, bathing, dressing, walking, toileting, and transferring, the IADL trajectories include; shopping, housework, meal preparation, taking medications, and managing finances, and the mobility measures will include; walking a quarter mile, climbing a flight of stairs, or lifting/carrying a 10lbs. The final mobility activity included is if the participant drove a car in the past month, where disability is defined as having not driven. In addition to these 16 measures, the patients will undergo the EQ-5D-5L [APPENDIX H]. The EQ-5D-5L²⁶ is a brief 5 question assessment that captures disability in self-care, mobility, and usual activities. It uses a scoring scale from 3, meaning no disability to 15 points, indicating severe disability. This tool has been mapped to the EORTC-QLQ-C30,²⁷ specifically in patients with advanced NSCLC²⁸. However, the EQ-5D-5L has been shown to be the preferred assessment due to its shortened length and its improved sensitivity and face validity.²⁶

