6.2 Secondary Endpoints

Functional trajectories and resiliency will be evaluated using generalized linear mixed models (GLMMS). This model allows for the estimation of intercept and slopes at both the individual and sample level. GLMMs can determine whether factors affect all patient trajectories in similar ways or whether they affect individual trajectories differently. To allow for possible changes in functional status over time (e.g., a change-point analysis) the ‘segmented’ package in R will be used.^{43,44} Participants’ functional status scores will be modeled using a segmented mixed model with random change points. Estimating the change point identifies the point in time that patients’ functional status scores change during the 12-months post-diagnosis. We anticipate that the start of treatment will be a change point depending on treatment tolerability vs. toxicity. This model allows for random and fixed effects, permitting analysis of between-subject and within-subject variance in longitudinal observations.

Resiliency will be defined as the ability to maintain or regain at least 50% of baseline functional status at any point during the 12 months after diagnosis with specific emphasis at 3 and 6-months post- the start of treatment. The association between resiliency and clinical factors will be evaluated with appropriate statistical techniques for the specific measure (e.g. Chi-square tests will compare categorical variables between participants demonstrating resiliency vs. worsening functional status; a two-sample t-test or Wilcoxon Rank Sum test will compare continuous variables). We will characterize differences in resiliency within each of these pre-defined groups. GLMMs will test for differences in resiliency between these groups. Models will be adjusted for important clinical and demographic variables. The data obtained from the primary endpoint will be used to refine the timing and duration of the pilot intervention as described in our secondary endpoint. Using GLMMS we will compare functional status in the 24-week follow-up period using both functional status measurement strategies to inform the survey design of a larger intervention trial.

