#A3802) and random hexamer primers (Invitrogen #588875) as directed by the manufacturers. p16 levels will be measured using a Taqman-based quantitative RT-PCR methods essentially as described by Liu et al. (20). Validated Taqman-based controls for T-cell purity (CD3G, Applied Biosystems #4331182 Hs00962186), sample viability (p14ARF, Applied Biosystems #4351370 HUMP14-ARF3) and RNA quantity (YWHAZ, Applied Biosystems #4331182 Hs03044281) are included in this analysis. Data clean up: Data will be filtered to exclude relatively invariant features (IQR = 0.5) and features below the detection threshold (defined for each sample by a cutoff corresponding to approximately twice standard deviation of negative control probes plus the mean of them) in at least half of the samples. Basic analysis Using R/Bioconductor and the filtered dataset, linear models for microarray data analysis⁴⁷ will be employed with a contrast matrix for the comparisons. P values will be used to rank miRNAs and mRNA of interest, and correction for multiple comparisons will be done by the Benjamini-Hochberg method.⁴⁸

Assessment*:	Screen	Visit 1 (Baseline)	Every Treatment Visit	Visit 2 (4 weeks)	Visit 3 (7 weeks)	Visit 4 (10 weeks)	Visit 5 (13 Weeks) End of intervention	Visit 6 (24 weeks)	Follow up to 24 months (2 years)
Signed Informed Consent	x								
Inclusion/Exclusion	x								
Medical & Cancer History	x								
Sociodemographic		x							
Disease Assessments		x						x	
Physical Exam		x			x		x	x	
Vital Signs		x			x		x	x	
SPPB		x			x		x	x	
2-6 MWT		x			x		x	x	
PROMIS-10		x			x		x	x	
Blood Chemistry		x			x		x	x	
Biomarker Testing (blood and stool)		x			x		x	x	
Functional Status Assessments		x	x	x	x	x	x	x	
PROMIS-10		x		x	x	x	x	x	
GAD-7		x		x	x	x	x	x	
PHQ-9		x		x	x	x	x	x	
EORTCQLQ-30		x		x	x	x	x	x	
EORTC LC-13		x		x	x	x	x	x	
POMS-12		x	x	x	x	x	x	x	

Toxicities/ Disease Response		X		X	X	X	X	X	
Survival Status									X
Semi-structured interview							X		

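### The note under the section 4.3 assessment table can be read as omitting the EQ-5D-5L at baseline, which conflicts with the rest of the protocol and needs reconciling

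*Combined protocol and SAP*

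**What the plan says.** The assessment table printed in section 4.3 is headed "ROAR-LCT Study Assessments (Baseline, Weeks 7, 13, and 24" and has a single row for the two functional status surveys, "EQ-5D-5L & 16 item Functional activity scale". Directly beneath the table stands the note "EQ-5D-5L performed every 3 weeks Not assessed at baseline".

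Three other places bear on the baseline:

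- Section 4.1: "Patients enrolled in this study will complete baseline assessments consisting of demographic information, disease assessment, functional status assessments". No instrument is named.
- Section 4.6, on functional status assessments, describes the 16-item survey (Appendix G) and continues: "In addition to these 16 measures, the patients will undergo the EQ-5D-5L" (Appendix H).
- The study calendar (section 8.0; in the text supplied, the table is printed just before that heading) has a row "Functional Status Assessments" marked at Visit 1, at every treatment visit and at Visits 2 to 6. It has no separate EQ-5D-5L row.

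Section 6.2 uses the scores in two ways. Resiliency is the ability to "maintain or regain at least 50% of baseline functional status", with no instrument named. The two surveys are also to be set against each other: "Using GLMMS we will compare functional status in the 24-week follow-up period using both functional status measurement strategies", so as to inform the survey design of a larger trial. Section 4.1 adds triggered assessments when either survey shows a decline in function. It does not say what the decline is measured against.

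**The concern.** The note is the only line in the document that names the EQ-5D-5L and speaks of its baseline. A note under a table normally states an exception to that table, so a coordinator could reasonably follow it and skip the questionnaire at Visit 1. The general wording elsewhere would not clearly stop this. Section 4.6 gives the EQ-5D-5L as an addition to the 16-item survey, so the calendar row could be taken to mean the 16-item survey alone.

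A pre-intervention score that was not taken cannot be recovered later. The EQ-5D-5L is one of the two measures that section 6.2 compares to help design the next trial. If it lacked the pre-intervention point, early movement away from the starting state would be visible on one measure and not on the other.

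**Working it through.** The plan states no figure on this point. The check is a cross-reading of the schedule, a count of visits, and a look at which analyses need the baseline score.

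**1. The places side by side**

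| Place | Bearing on a baseline EQ-5D-5L |
|---|---|
| 4.3 table header and row | Baseline listed; EQ-5D-5L shares a row with the 16-item scale: for |
| 4.3 note, read as one statement | Against |
| 4.1 baseline battery | Functional status assessments, in the plural, instruments not named: for, but general |
| 4.6 | EQ-5D-5L placed under functional status assessments: for |
| Calendar, Visit 1 | Functional status marked, no EQ-5D-5L exception: for, but no separate row |

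**2. Does moving the note to another row clear the conflict?** Not fully. Each entry in the 4.3 table has a calendar row: SPPB, walk test, functional status, GAD-7, PHQ-9, PROMIS-10, blood and stool, toxicity and disease response (one combined row), the two EORTC questionnaires, and POMS. All of these rows are marked at Visit 1. Wherever the phrase about baseline is attached, it disagrees with the calendar as printed.

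**3. Dated visits (study calendar)**

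- With baseline: Visit 1 and weeks 4, 7, 10, 13 and 24 = 6.
- With the note applied to the EQ-5D-5L: weeks 4, 7, 10, 13 and 24 = 6 − 1 = 5.
- On the four time points in the table header alone: 4 − 1 = 3.

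The calendar also marks functional status at every treatment visit. If that row includes the EQ-5D-5L, some patients could have a score before week 4. That would still not supply a scheduled pre-intervention score.

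**4. What depends on the missing score.** Write Y(0) for the score at Visit 1 and Y(t) for a later score.

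- Change from baseline is Y(t) − Y(0). Without Y(0) it is undefined on the EQ-5D-5L at every t.
- Resiliency compares Y(t) with 50% of baseline function. It also needs Y(0), so it cannot be classified on the EQ-5D-5L. On the 16-item scale Y(0) exists and the classification stands.
- The worsening trigger needs some earlier score. The first EQ-5D-5L has none, so it cannot fire the trigger. From the second score on, a comparison with the previous one is possible.
- The mixed-model comparison can be fitted on the five shared dated visits. It loses the pre-intervention point on one measure.

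**The case against.** The strongest reply is that the note is not one statement. It has no punctuation and a capital letter in mid-line, and any footnote markers may have been lost when the text was read from the PDF. It could be one note on EQ-5D-5L frequency and a second that belongs to another row, such as disease response. The table header, sections 4.1 and 4.6 and the calendar together schedule a baseline EQ-5D-5L. If they govern, none of the consequences above arises. This stands as a reason not to treat the omission as established. It does not remove the need to reconcile, because the line as printed can mislead and no EQ-5D-5L calendar row corrects it.

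A reader might also infer more than the documents support:

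- *That the resiliency endpoint fails.* Section 6.2 names no instrument, and the 16-item scale has its baseline.
- *That the trigger is disabled.* Section 4.1 states no baseline reference. Only the first EQ-5D-5L score is affected.
- *That the comparison of surveys cannot be made, or would favour the 16-item scale.* It is defined over the 24-week follow-up and can use the shared visits. The direction of any distortion is not shown.
- *That the first EQ-5D-5L is always at week 4.* The mark at every treatment visit leaves room for an earlier score.
- *That the sponsor chose to drop the baseline.* The text shows an inconsistency, not a decision.

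**Conclusion.** The concern holds as an internal inconsistency with a conditional consequence. If the note is read as applying to the EQ-5D-5L and is followed, every participant lacks a scheduled pre-intervention score on one of the two measures in section 6.2, and that measure has 5 dated visits against 6. Change from baseline and resiliency on the EQ-5D-5L could then not be computed, and the loss could not be repaired later. If the header, sections 4.1 and 4.6 and the calendar govern, nothing is lost.

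The document does not decide between the two readings. The visit count assumes the calendar columns were read correctly from the PDF and covers dated visits only. The primary feasibility endpoints do not use the EQ-5D-5L score as a reference. The matter is still worth correcting because a stated secondary comparison depends on it and the remedy is small.

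**What to change.** 1. In section 4.3, state which row the remark about baseline applies to, and remove it from the EQ-5D-5L. If it belongs to another row, reconcile it with that row's Visit 1 mark in the calendar.
2. Add an EQ-5D-5L row to the study calendar, marked at Visit 1 (completed before the first physical therapy and relaxation session) and at weeks 4, 7, 10, 13 and 24.
3. State in section 6.2 that the two functional status measures are compared on the same visits, Visit 1 included.

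The cost is one five-item questionnaire at a visit that already includes surveys, a corrected table note, one calendar row and one sentence in section 6.2.
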